We will conduct an exploratory analysis to examine if access to home and community health services predicts healthcare utilization in the 6 months after an ED visit at the end of life. We will examine correlations between home and community health access factors and healthcare utilization from the 18 healthcare systems included in the PRIM-ER study using the Senior Care Services Scale (SCSS) developed by Arbaje et al.³² Data from all 18 healthcare systems collected from the Grey Literature Review and Qualitative Interviews will be eligible for this exploratory analysis.

Contextual factors from the Grey Literature Review and the Qualitative Interviews will be used to analyze if access to home and community health services predicts healthcare utilization. Healthcare utilization data will be provided from the PRIM-ER study and will be collected from Medicare claims data to include ED revisits (count), inpatient days (count), home health use (Yes/No), and hospice use (Yes/No) in the 6 months from the index PRIM-ER ED visit. These measures of healthcare utilization are based on the Dartmouth Atlas Decedent Cohort Care Intensity Measures to monitor the quality of end-of-life care in Medicare patients. The SCSS will be adapted to PRIM-ER using contextual factors from the Grey Literature Review and Qualitative Interviews 2. Each healthcare system will be assigned a score based on their access to home and community health services.

B) Inclusion and Exclusion Criteria

Eligible patients will include ED patients 66 years or older with serious, life-limiting illness who visited any of our EDs during the implementation of PRIM-ER. Patients must demonstrate one-year mortality of at least 30 percent (score > 6) according to the Gagne Index, a validated instrument used to measure all cause one-year mortality in community-dwelling older adults, calculated based on their prior 12 months before the index ED visit of Medicare claims. ED patients transferred from a nursing home on the index ED visit will be excluded since prediction of mortality and disposition of such patients differs from community-dwelling adults. Patients currently receiving hospice at the time of the index ED visit will also be excluded since they have already received services.

Qualitative Interviews Contextual Assessment

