Table 1 outlines the independent variables. Independent variables were previously assessed at the time of site implementation. Healthcare system- and provider-level variables were collected by the project manager and via a provider survey at the level of each participating ED. Patient-level variables will be assessed using the CMS Research Data Assistance Center Master Beneficiary Summary File, Base (A/B/D) Segment. The Project Manager will also document if trainings occurred via in-person or virtually to understand more deeply the implementation of the QI initiative at each site.

Table 1. Independent Variables			
Variable	Coding	Source	
Implementation Period	Weeks from Time 0	Project Manager	
Healthcare system/ED-level variables			
Health System	Allegheny, Bay State, Beaumont, Brigham and Women's, Christiana Care, Henry Ford, [name] Anderson, NYU Langone, Ohio State University, Ochsner, Rutgers, Sinai, UC San Francisco, University of Florida, University of Pennsylvania, University of Utah, Yale New Haven	Project Manager	
ED	1—35	Project Manager	
ED Volume	30,000—49,999 visits, 50,000—69,999 visits, 70,000—89,999 visits, ≥ 90,000 visits	Project Manager	
Ownership	Nonprofit, Government, For Profit	Project Manager	
Emergency medicine residency training site	Yes/No	Project Manager	
Free-standing ED	Yes/No	Project Manager	
Dedicated ED social worker/care manager	Yes/No	Project Manager	
US Region	Northeast, Midwest, Southeast, Southwest, West	Project Manager	
Metropolitan Status+	Yes/No	Project Manager	
Outpatient palliative care	Yes/No	Project Manager	
EHR	Epic, Cerner	Project Manager	
Trauma center	Yes/No	Project Manager	
Patient variables			

Age	Years	Master Beneficiary Summary File, Base Segment
Gender	Female, Male, Other	Master Beneficiary Summary File, Base Segment
Race/Ethnicity	Asian, Black, Hispanic, White, North American Native, Unknown, Other	Master Beneficiary Summary File, Base Segment
Gagne index ²⁴	Count of conditions	Inpatient and outpatient RIF
+Population estimates by MSA are based on estimates of the civilian non-institutionalized population of the US as of July 1, 2013, from the 2013 National Health Interview Survey, National Center for Health Statistics, compiled according to the 2013 Office of Management and Budget definitions of core-based statistical areas. See http://www.census.gov/population/metro/ for more about metropolitan statistical area definitions.		

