For the PRIM-ER Contextual Assessment that data analysis will vary per specific component.

Grey Literature Review: Data will be collected and analyzed on the regional, state, and healthcare system level. Data will be coded and collated per topic of interest. A combination of descriptive statistics, narrative description, and thematic coding will be used to summarize and present the data.

Qualitative Interviews: For the qualitative data, the interview transcriptions will undergo verbatim transcription and thematic coding. We will develop deductive codes based on the discussion guide, and inductive codes based on salient topics identified during review and coding of the transcripts. We will compare codes across all of the transcripts during the final analysis phase and condense codes into meaningful categories. We will use ATLAS.ti software to facilitate coding as well as cross-investigator and cross-interview analyses. We will also develop data matrices to highlight prominent themes related to facilitators and barriers to home and community health services. For quantitative analysis, we will use descriptive statistics to summarize the data.

Exploratory Analysis: This exploratory analysis will mirror the healthcare utilization analysis and statistical model described in the PRIM-ER. Each healthcare system index score will be used as an independent variable in our predictive model to determine the relationship between home and community health access factors and healthcare utilization in the 6 months after an ED visit at the end of life.

The healthcare system dependent (Ea.) and independent variables (Eb.) described above for PRIM-ER grant will also be used for the analysis of the PRIM-ER Contextual Assessment.

c. Methods

The analytic plan accounts for the nested structure of the data, assesses normality assumptions of dependent variables, and addresses issues related to missing data, study participation bias, and baseline covariate balance. We address each of these in turn. All analyses will be conducted in R 3.3.2 (R Foundation for Statistical Computing, Vienna).

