Prior to conducting the outcome analyses, we will compare patients in each ED cluster with respect to patient, provider, and facility characteristics. We will assess whether any adjustments will need to be made in the final statistical models based on whether the differences are clinically meaningful. To account for nesting in the data structure (patients nested in hospitals), we will use mixed effect multi-level models to estimate effect sizes. We anticipate two sources of variation.

The **primary outcome** is the proportion of eligible patients whose disposition is to an acute care setting (inpatient, non-palliative service). The **secondary outcomes** include healthcare service utilization in the 6 months following the ED visit and survival times following the ED visit. The health utilization outcomes include receipt of ED revisits (count), home health services (yes/no), inpatient days (count), admission to an ICU

(yes/no), and admission to hospice (yes/no). The analysis of the effect of PRIM-ER on ED disposition in the context of a stepped-wedge design will be based on a Generalized Linear Mixed Model (GLMM). In particular, to assess the intervention effect, we will use a generalized linear binomial model with random site level effects. The analysis of site, provider, and patient-level characteristics that are associated with variation in impact of PRIM-ER will be based on extending the models used in the analysis plan for ED disposition, healthcare utilization in 6 months following the ED visit, and survival times to include independent variables related to the characteristics of interest.

5. Risks to Subjects

Any information collected from Emergency Department providers will be utilized solely for QI purposes and not analyzed for research.

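### The access-score analysis does not say how Health System enters the model: as a fixed factor it absorbs the score, and if left out it makes the score's standard error too small

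*Combined protocol and SAP*

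**What the plan says.** All references are to the combined protocol and SAP.

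- **Level of the score.** The Exploratory Analysis text before the inclusion criteria says: "Each healthcare system will be assigned a score based on their access to home and community health services". All 18 systems contribute: "Data from all 18 healthcare systems collected from the Grey Literature Review and Qualitative Interviews will be eligible for this exploratory analysis".
- **Role of the score.** Under Data Analysis (section E), the Exploratory Analysis paragraph says: "Each healthcare system index score will be used as an independent variable in our predictive model". The analysis is to mirror the PRIM-ER utilization model.
- **Other variables.** The next paragraph says: "The healthcare system dependent (Ea.) and independent variables (Eb.) described above for PRIM-ER grant will also be used for the analysis". The sentence goes on to name the Contextual Assessment and excludes no variable.
- **What those variables are.** Part b of section E says: "Table 1 outlines the independent variables". The first healthcare-system row of that table is "Health System Allegheny, Bay State, Beaumont" and so on, a list of named categories. ED, numbered 1 to 35, is the next row.
- **Random structure.** Part c (Methods) describes multilevel mixed models with patients nested in hospitals, and for ED disposition it specifies random effects at site level. It leaves covariate adjustment to a later comparison of ED clusters.

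The documents never say whether Health System is fixed, random or left out when a system-level score is the predictor. They state no power or precision for this analysis.

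**The concern.** The score cannot vary between two EDs of the same system. All the information about it therefore lies in differences between systems, and what the model does with Health System decides whether the score can be estimated and how precise it appears.

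Two readings are open. On the first, Table 1 is carried over with Health System as an ordinary categorical covariate. The system indicators then explain every between-system difference and leave nothing for the score. Software would drop either the score or one system indicator, and in the second case the printed coefficient only contrasts systems. On the second, the analyst copies the site-level random effect from the Methods and omits Health System. The score then gets a coefficient, but the model treats 35 EDs as independent evidence on a quantity that has at most 18 values.

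The relation of access to utilization is the only question this analysis asks. It would get either no answer or an overconfident one.

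**Working it through.** There is no figure in the plan to reproduce, so the check has two parts: identifiability, then error rate.

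**Inputs from the documents.** 18 systems; 35 EDs; over 57,000 patients, so about 57,000 / 35 = 1,629 per ED; one score per system.

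**Inputs assumed.** SD between EDs within a system τ_e = 0.2 on the logit scale; SD between systems τ_s from 0 to 0.5; event variance p(1 − p) = 0.21 for a yes/no outcome; the split of EDs over systems. The rank results need none of these.

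**1. Identifiability.** Let D_is = 1 if patient i belongs to system s, and let a_s be that system's score. The score column is x_i = Σ_s a_s D_is, an exact linear combination of the indicators.

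| Fixed part of the model | Columns with score | Rank with score | Score identified |
|---|---|---|---|
| 18 system indicators, ED random | 19 | 18 | no |
| Intercept, one patient and one period covariate, 17 system contrasts | 21 | 20 | no |
| Intercept only, ED random | 2 | 2 | yes |

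Making ED random does not help while Health System stays fixed. With both as random intercepts the score is identified.

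**2. Error rate if Health System is omitted and only ED is random.** The sampling variance of an ED's estimate is v = 1 / (1,629 × 0.21) = 0.0029. The correlation between two EDs of one system is

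ρ = τ_s² / (τ_s² + τ_e² + v).

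For a predictor that is constant within system, the true variance of the slope exceeds the model's by about 1 + (n* − 1)ρ. Here n* = Σn² / Σn, with n the number of EDs in a system. A nominal 5% test then rejects a true null with probability of about 2Φ(−1.96 / √inflation).

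With an equal split, n* = 35 / 18 = 1.94:

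- τ_s = 0.1: ρ = 0.01 / 0.0529 = 0.189; inflation 1 + 0.944 × 0.189 = 1.18; SE too small by a factor of 1.09; rejection about 7%.
- τ_s = 0.5: ρ = 0.25 / 0.2929 = 0.853; inflation 1 + 0.944 × 0.853 = 1.81; factor 1.34; rejection about 14%.

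Uneven splits make it worse. If six systems had 5, 5, 4, 3, 3 and 3 EDs and twelve had one each, n* = (25 + 25 + 16 + 9 + 9 + 9 + 12) / 35 = 105 / 35 = 3.0. At τ_s = 0.5 the inflation is 1 + 2 × 0.853 = 2.71, the factor 1.65 and the rejection rate about 23%.

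Null simulations with an ED-level linear approximation, a Wald test and two assumed splits agree: about 5% to 6% at τ_s = 0, 8% to 9% at τ_s = 0.1, and 12% to 23% at τ_s = 0.2 to 0.5.

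**3. With system and ED both random.** For one assumed split, the standard error per SD of score is 0.036, 0.043, 0.080 and 0.124 at τ_s = 0, 0.1, 0.3 and 0.5. Precision is governed by the number of systems: 18 − 2 = 16 degrees of freedom for the score alone. If the four US Region contrasts are added and region is constant within system, 16 − 4 = 12 remain.

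**The case against.** The strongest reply is that the documents nowhere say Health System is coded as fixed indicators. Table 1 is a list of variables, not a model formula. The sentence that carries it over speaks of the Contextual Assessment as a whole. The Methods use mixed models and leave adjustment open, and a rank-deficient fit would be noticed at once and respecified without new data. This stands in part. A reader might infer that the score coefficient cannot be estimated under the plan as written. That follows only from fixed coding, which the text suggests but does not state. What the reply does not do is supply a correct model. The random effect in the Methods is at site level, and no passage makes Health System a grouping factor. Omitting it leads to the understated error above, and no software warning would reveal that.

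Other stronger readings are also unsupported:

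- **ED absorbs the score as well.** Only if ED were a fixed factor. The Methods treat site as random, and a random ED intercept does not alias a system-level score.
- **The planned analysis of site, provider and patient characteristics has the same fault.** The Methods extend the models "to include independent variables related to the characteristics of interest", but the question there is variation in PRIM-ER's impact. Each ED contributes data from before and after implementation, so an interaction of intervention with an ED characteristic varies within ED and is identified.
- **Table 1 has as many parameters as there are EDs.** This assumes that every listed variable enters at once, which the Methods do not say. It also counts region on top of system, although region adds no rank if it is constant within system.

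That the analysis is exploratory is a fair limit on how much this matters.

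**Conclusion.** The point holds as an underspecified model with a definite consequence on each open reading. With Health System fixed, the score has no separate coefficient; this is exact and rests on no assumption beyond one score per system. With Health System omitted and ED random, the score's standard error is too small whenever outcomes vary between systems. The illustrative size is 8% to 23% rejection against a nominal 5%, for assumed system SDs of 0.1 to 0.5 and an ED SD of 0.2 on the logit scale. If systems did not differ beyond their EDs, there would be almost no inflation. The documents give no variance components, so where this trial lies in that range is unknown.

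The extracted Table 1 shows 17 system names where the text says 18. This may come from the PDF reading and changes nothing here. The effect is confined to one exploratory analysis.

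**What to change.** In the Exploratory Analysis paragraph of section E, state that for the access-score analysis:

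1. Health System is not a fixed covariate. It enters as a random intercept with ED nested in it.
2. Inference on the score uses between-system degrees of freedom: at most 18 systems, about 16 for the score alone and fewer with each further system-level covariate. Default Wald z-tests from a mixed model do not do this. A t reference on those degrees of freedom, or a second-stage regression of adjusted system-level estimates on the score, would.
3. The result is reported as a descriptive between-system association resting on 18 systems, not on more than 57,000 patients.

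The cost is one paragraph and no new data. The downside is a wider interval for the score. A short prespecified covariate list, or scoring services per ED so that the score varies within multi-ED systems, would be optional refinements; the second needs extra desk work and departs from the plan's choice to score systems.

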We propose the implementation and testing of a novel, highly efficient pragmatic intervention that seeks to shift the clinical practice paradigm of emergency medicine. We propose a pragmatic, cluster-randomized stepped wedge design to test the effectiveness of primary palliative care education, training, and technical support for emergency medicine (PRIM-ER) in 35 Emergency Departments (EDs). PRIM-ER includes four core components: 1) evidence-based multidisciplinary primary palliative care education, 2) simulation-based workshops on communication in serious illness, 3) clinical decision support, and 4) provider audit and feedback. These core components will be implemented in each participating health system as part of a quality improvement initiative to improve the care older adults with serious illness receive in the ED setting. In the UG3 phase of the project, we will: 1) tailor PRIM-ER to the emergency provider workforce and a more diverse ED context using an agile implementation framework approach; and 2) pilot test PRIM-ER at two sites for feasibility, fidelity, and usability. In the UH3 phase, we will: 3) implement PRIM-ER in a cluster-randomized, stepped wedge design in the remaining 33 EDs; and 4) measure the effect of PRIM-ER on aspects of: a) ED disposition to an acute setting; b) healthcare utilization in the 6 months following the ED visit; and c) survival following the index ED visit. The project will thus be implemented in a total of 35 EDs (2 pilot sites and 33 remaining EDs) as previously approved and outlined in the below table. We hypothesize that it will be feasible to test PRIM-ER at two EDs with a high level of fidelity and usability and implement at all sites. We also hypothesize that older adult visitors with serious, life-limiting illness cared for by providers with primary palliative care skills will be less likely to be admitted to an inpatient setting, more likely to be discharged home or to a palliative care service, and will have higher home health and hospice use, fewer inpatient days and ICU admissions at 6 months, and longer survival than those seen prior to implementation. Additionally, we hypothesize that sites with higher baseline ED disposition to an acute care setting and less primary palliative care knowledge and skills will demonstrate greater change after implementation.

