This is a cluster-randomized QI initiative that will implement and test the impact of PRIM-ER in various healthcare settings. We will first develop and pilot test the QI initiative at two sites in the UG3 phase, and then use a cluster-randomized, stepped wedge design to implement the education, training, and technical support in our network of EDs in the UH3 phase. Randomization will occur at the ED level and be done in advance by the biostatistician to determine the order in which the training will occur. Due to the COVID-19 pandemic, training will occur either in-person or virtually. The virtual trainings will occur using NYULH's Zoom account, meeting ID and set password. A member of the PRIM-ER team will be on each virtual training in order to monitor learner's attendance and assist with any technical glitches. The PRIM-ER team will provide the training link, meeting ID, and password to each Site Principal Investigator (PI) and the Site PI will distribute the link and meeting ID accordingly to his/her staff at their own home institution. Reminder e-mails about the training will be sent from each Site PI to his/her staff. The overall approach involves ongoing asynchronous learning and technical support to bolster skills, conduct interdisciplinary case reviews, and reinforce clinical pathways and protocols via provider audit and feedback. Electronic triggers for palliative care will be embedded in the electronic health record (EHR) to identify patients who may benefit from hospice or palliative care services. These electronic triggers already existing in the Perelman Center for Emergency Services EHR as part of standard, clinical workflow, but will be further tailored for each participating health system. Palliative care champions at each site will facilitate attendance at didactic and workshop sessions, disseminate information about local resources for outpatient palliative care, home care and hospice, and work with the local informatics team to reinforce protocols and implement trigger criteria to identify older adults who may benefit from further needs assessment and follow-up. We will engage with the palliative care champions to better understand the QI implementation process including but not limited to obtaining champion's feedback on the initiative, suggestions for improvements, and adaptations- all which are common approaches in implementing and reflecting on QI initiatives. Engagement will be in the form of discussions post QI about what went well, and what can be improved upon in moving forward as well as understanding from the champion's perspective what they could have done differently so the project team can gather lessons learned. Physicians and nurses will receive audit and feedback reports to monitor their performance over time, and a learning monitoring system will track participation in educational activities.

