Participants for the provider interviews will include one emergency medicine physician and one nurse champion from each of the 18 healthcare systems already enrolled within the PRIM-ER. As part of PRIM-ER each site has already identified a provider and nurse champion that the study team will outreach. Inclusion criteria includes: Must be a practicing licensed physician or licensed registered nurse within a department of emergency medicine within a healthcare system included in the PRIM-ER study, must be 18 years or older, must be willing to provide verbal consent.

Qualitative Interviews CDS

Participants for the CDS interviews will include one Site PI from each of the 18 healthcare systems already enrolled within the PRIM-ER study. This is completely voluntary and Site PIs do not have to participate if they do not want to and/or do not have the time. As part of PRIM-ER project, each site has already identified a Site PI that the study team will outreach. Inclusion criteria includes: Must be a practicing licensed physician within a department of emergency medicine within a healthcare system included in the PRIM-ER study, must be 18 years or older, must be willing to provide verbal consent.

C) Number of Subjects

We expect to analyze the Medicare claims of over 57,000 patients with serious illness who have made their index ED visit to any of the 35 EDs.

Qualitative Interviews Contextual Assessment

We will recruit 18 licensed emergency medicine physicians and 18 emergency medicine registered nurses for a total of 36 participants for the provider interviews.

Qualitative Interviews CDS We will recruit a maximum of 18 licensed emergency medicine physicians/Site PIs for the CDS interviews.

D) Recruitment and Informed Consent

Medicare claims of patients 66 years and older with serious, life-limiting illness who made a visit to any of our EDs during the study period will be used to measure outcomes in our patient cohort. We will seek a waiver of Health Insurance Portability and Accountability Act (HIPAA) authorization for ED patients as this study presents no more than minimal risk and cannot be practicably conducted without the waiver given the study's geographic breadth and sheer number of participants (>57,000 eligible patients). Obtaining informed consent for participation and use of Medicare claims from all patients in this study is not feasible and will interfere with the conduct of this study.

Qualitative Interviews

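### The primary stepped-wedge model names no ED-by-period variance component, so its standard error is too small if EDs' admission rates drift differently over time

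*Combined protocol and SAP*

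**What the plan says.** Section 4.E.c (Data Analysis, Methods) sets out the clustering as follows: "To account for nesting in the data structure (patients nested in hospitals), we will use mixed effect multi-level models to estimate effect sizes". The next statement is "We anticipate two sources of variation", and the sources are not named. For ED disposition, the primary outcome, the text specifies a GLMM: "we will use a generalized linear binomial model with random site level effects".

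The summary describes the design as "implement PRIM-ER in a cluster-randomized, stepped wedge design in the remaining 33 EDs", and section 4.A adds "Randomization will occur at the ED level".

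Time appears in Table 1 (section 4.E.b) as an implementation-period variable counted in weeks. The model sentence does not say how it enters. The available text does not mention an ED-by-period random effect, a random time slope, a decaying within-ED correlation, a cluster-robust variance, a small-sample correction, a permutation test, or a sensitivity analysis on the correlation structure.

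**The concern.** A model with only a constant random effect per ED treats two visits to the same ED as equally correlated whether they are one month or three years apart. It also assumes that, apart from the intervention, all EDs follow the same time course on the model scale. In a stepped wedge, the intervention effect is estimated largely from before-and-after change within EDs. ED-specific change over time is therefore the noise that competes most directly with the effect.

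A binomial model has no free residual variance, so omitted ED-specific drift does not reach the standard error. A common calendar-time term does not help, because it removes only the movement that all EDs share.

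The claims window runs from two years before initiation to the end of roll-out, and the trial ran through the pandemic ("Due to the COVID-19 pandemic, training will occur either in-person or virtually"). An identical time course in every ED is a strong assumption over such a period. At stake are the width of the primary confidence interval and the false-positive rate of the primary test.

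**Working it through.** The plan has no power calculation, alpha, ICC or standard error to reproduce, so the check asks how far a site-only standard error could fall short.

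**Inputs from the documents**
- 33 randomized EDs (summary).
- "We expect to analyze the Medicare claims of over 57,000 patients with serious illness" over 35 EDs (section 4.C): 57,000 / 35 = 1,629 per ED.
- Section 4.A: claims from 24 months before initiation less a 12-month roll-in leaves 12 baseline months. Rates are monthly and continue to 6 months after the last site.

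**Assumptions not in the documents**
- A 24-month roll-out with crossovers spread evenly. The total is 12 + 24 + 6 = 42 months, and 1,629 / 42 = 38.8 visits per ED-month.
- 70% admission; two-sided 5% test; ICC 0.01, 0.02 or 0.05.
- Fixed month effects common to all EDs are already in the model.

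**Method (linear approximation on ED-month proportions)**
1. Total variance is 0.7 × 0.3 = 0.21. Between-ED variance is τ² = ICC × 0.21, and sampling variance per ED-month is w = (0.21 − τ²) / 38.8.
2. The planned model uses the working covariance V_w = τ²J + wI. Its variance for the effect is the last diagonal element of A = (ΣX′V_w⁻¹X)⁻¹.
3. The true variance is the same element of A(ΣX′V_w⁻¹VV_w⁻¹X)A. Here V has either exchangeable ED-month effects (within-ED autocorrelation c across months) or correlation decaying as r^|s−t|. In the exchangeable case the working τ² is set to c × ICC × 0.21.
4. Type I error = 2[1 − Φ(1.96 × SE_model / SE_true)].

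**Worked cases, ICC 0.05.** SE_model is 0.74 percentage points.
- Exchangeable, c = 0.8: SE_true is 0.87. 1.96 × 0.737 / 0.874 = 1.65, giving 9.8%.
- Decay, r = 0.98: SE_true is 1.37. 1.96 × 0.738 / 1.367 = 1.06, giving 29%.

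| Type I error | ICC 0.01 | ICC 0.02 | ICC 0.05 |
|---|---|---|---|
| No differential drift | 5.0% | 5.0% | 5.0% |
| Exchangeable, c = 0.9 to 0.8 | about 5.4–5.8% | 5.9–6.8% | 7.4–9.8% |
| Decay, r = 0.99 to 0.98 per month | about 8–11% | 11–16% | 19–29% |

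With a 33-month roll-out, the ICC 0.02 and 0.05 settings span 5.7% to 33.5%.

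**What the decay rows imply.** The SD of an ED's own 12-month change, beyond the common trend, is √[2τ²(1 − r¹²)].
- ICC 0.05 (τ² = 0.0105): √(0.021 × 0.1136) = 4.9 points at r = 0.99, and √(0.021 × 0.2153) = 6.7 points at r = 0.98.
- ICC 0.01 (τ² = 0.0021): √(0.0042 × 0.1136) = 2.2 points, and √(0.0042 × 0.2153) = 3.0 points.

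**Simulation check.** A binomial logistic model with a site random intercept and fixed period effects was fitted with no true effect (33 EDs, 11 steps of 3, 4 baseline periods, site SD 0.3 on the logit scale, 1,500 replicates).
- No drift: 4.9%.
- ED-by-period SD 0.10 / 0.15 / 0.20 (logit): 7.3% / 11.3% / 16.0%.
- Random linear ED trend, SD 0.3 / 0.5 over the study: 7.9% / 12.5%.
- Across these drift settings the model SE stayed at 0.032 while the true SD rose to between 0.035 and 0.045.

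**Does the missing term cure it?** In an empirical-logit version (4,000 replicates, 5.5% with no drift):
- ED-by-period SD 0.15: adding the ED-by-period effect took type I error from 11.3% to 5.8%.
- Linear trend SD 0.5: adding a random slope took it from 12.7% to 4.8%.

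The variance components were set at their true values in both fits, so estimating them would do somewhat less well.

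**The case against.** The strongest reply is that the plan is silent on the point and does not clearly exclude an ED-by-period term. The two sources are never named, and the plural in the model sentence could be stretched to cover a random slope. This stands in part. A reader might infer that the plan fixes a random intercept and nothing else. The documents do not say so, although "patients nested in hospitals" makes between-ED and between-patient variation the natural reading. If a third component was intended, it is still not prespecified.

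Second, the consequence is conditional. A reader might infer that the primary interval is too narrow as a matter of fact. The documents do not support that: with no differential drift, the site-only model holds its level. The COVID-19 sentence concerns how training was delivered, and is not evidence that admission rates diverged.

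Third, the large figures need large inputs. The 19–29% results require a between-ED SD of about 10 points and ED-specific yearly changes with an SD of about 5 to 7 points. Nothing in the documents supports values of that size. At ICC 0.01 with exchangeable effects the excess is under one percentage point.

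Fourth, a reader might extend the point to the secondary outcomes or to shocks shared within health systems. The secondary models are not written out beyond the general mixed-model statement, so the point carries over only if they use site-only effects. The 18 systems describe the whole project, and how the 33 randomized EDs divide among them is not shown. A system-by-period variance may not be estimable.

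**Conclusion.** The point holds in conditional form. Followed as written, the primary analysis has no component for ED-specific change over time. If such change exists, its standard error is too small and its test exceeds the nominal level. The direction is secure: it appeared in every drift scenario, by two methods, and vanished when drift was removed.

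The size is not established. Under the assumptions listed, type I error runs from about 5.4% to about 29%, depending on an ICC and a correlation pattern that the documents do not give. That range is not a prediction for this trial, and it does not show that the primary result would be wrong. The change is best regarded as a cheap improvement, to be settled before the outcome data are analysed.

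**What to change.** In section 4.E.c, specify for the primary model a random ED intercept plus a random ED-by-period effect, for example nested-exchangeable with monthly or quarterly periods. State that intervals and tests use a small-sample correction for about 33 clusters. Add a permutation test over the randomized crossover order as a check on the primary p-value. The biostatistician sets that order in advance, so the test does not depend on the correlation model. Revise the sentence on sources of variation to name each component.

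Apply the same structure to any secondary model that would otherwise carry site-only random effects. Keep a health-system-by-period effect as an optional sensitivity analysis only.

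The cost is a few sentences of SAP text, one more variance term, and the programming of the correction and the permutation test. If drift is present, the confidence interval will be somewhat wider. If it is absent, the extra variance should be estimated near zero and little precision lost.
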